A comparative study of Vitamin D serum levels in monosymptomatic enuretic children and non-enuretic children

INTRODUCTION

Nocturnal enuresis is a widely prevalent problem. It occurs in up to 15% of 5-year-old children and 10% of 10-year-old, with a spontaneous remission rate of 14% per year. Bedwetting can have a considerably distressing social impact on children and subsequently their families, affecting children's self-esteem and interpersonal relationships, and their scholastic achievement.¹

Nocturnal enuresis is classified into monosymptomatic (MNE) and non-monosymptomatic (NMNE), depending on whether it is associated with voiding or storage symptoms or not. It can also be categorized into primary, which is since birth, and secondary enuresis, which is newly onset after at least 6 months of a previous asymptomatic state.²

Primary monosymptomatic nocturnal enuresis (PMNE) is the most frequent urologic complaint among pediatric patients; however, the pathology and etiology of this problem have not been clearly determined.³

Nocturnal bladder control is a matter of developmental delay. At 1 year of age, the conscious sensation of urinary bladder fullness starts to evolve and this physiological turning point allows the beginning of the development of voluntary control of voiding by the age of 2 years.⁴ By the age of 4 years, full daytime and nighttime urinary control is obtained by most children.⁵

The idea that enuresis is related to the immaturity of the central nervous system is supported by the finding that premature and/or low-birth-weight children experienced bed-wetting more often than normal-birth-weight children.⁶

Low nocturnal anti diuretic hormone (ADH) and urine osmolality play a role in MNE associated with Nocturnal Polyuria (NP), which doesn't occur as an isolated abnormality but is also linked to children who also suffer of arousal abnormality⁷. We have proved this in our previous study in which we stated that Nocturnal polyuria and decreased nocturnal urine osmolality were key factors in pathogenesis of nocturnal enuresis⁷.

There are many clinical observations that link nocturnal enuresis with developmental delay in language and physical growth⁸ and skeletal maturation.⁹ Nocturnal enuresis could be linked with sleep disorders as well.¹⁰

Vitamin D is important for bone growth and regulation of calcium homeostasis. It not only plays a vital role in skeletal growth but also has other critical biological actions in neural development and function.¹¹

The source of vitamin D is primarily sunlight; it is also found in few foods as oily fish and fortified margarine. Vitamin D consists of a cholesterol backbone and has steroid-like effects. It is the fat-soluble hormone that plays an essential role in brain health.¹²

Studies claim that vitamin D may have an essential role in sleep regulation¹³.

Vitamin D deficiency is linked with Obstructive Sleep Apnea (OSA)¹⁴ and nocturnal polyuria is one of the main adverse outcomes of OSA.¹⁵

Vitamin D deficiency could cause excessive urine production directly. This was shown in a study done on mice which showed that vitamin D deficiency leads to activation of the Renin Angiotensin system. Eventually the augmentation of renin synthesis leads to increased

plasma Ang II production from angiotensinogen, which drives mice to increase water intake and intestinal salt absorption, since Ang II is a very potent thirst-inducing agent that acts on the central nervous system, as well as a potent stimulator of intestinal sodium absorption. As a result, the mice must excrete more urine and salt to maintain volume and electrolyte homeostasis.⁽¹⁶⁾

AIM OF THE STUDY

To evaluate the relationship between Vitamin D deficiency and nocturnal enuresis, and to study the correlation between vitamin D deficiency and urine osmolality which is an indirect indicator of ADH deficiency.

PATIENTS AND METHODS

This is a case control study which was performed in Ain Shams University Hospitals. It was conducted in the period between February 2021 and August 2021.

Patient group: Sixty children aged from 5 to 15 with primary mono-symptomatic nocturnal enuresis were included and selected randomly.

Inclusion criteria: Patients with PMNE which was defined as bedwetting frequency of 3 or more nights per week for at least 2 weeks of observation, and who didn't receive any previous treatment for enuresis.

Exclusion criteria: Patients with non-monosymptomatic enuresis (associated with storage and/or voiding symptoms), anatomical abnormalities (Meatal stenosis, Hypospadias, Epispadias, etc.), neurological diseases, renal impairment, previous pelvic, urological or brain and spinal cord surgery, chronic constipation and irritable bowel habits, active urinary tract infection and patients who are on vitamin D supplements.

Control group: Sixty healthy children were included as a control group whose ages ranged from 5 to 15 years old, and they were chosen from apparently healthy non-enuretic children.

Written informed consent was obtained from patients' legal guardians, and the study was approved by Ain Shams University Ethical Committee.

Methods:

All children included in the study were subject for detailed medical and surgical history to rule out the presence of organic or psychological diseases. Physical examination including focused neurological examination to exclude neurological diseases, especially (neural tube defects) and local urological examination to check for any genital or external urethral meatus anomalies. Also urine analysis was done to exclude urinary tract infection.

Frequency Volume chart and nocturnal urine osmolality.

Volume Frequency chart was recorded for both enuretic and control groups, to evaluate frequency, average voided volume, and to exclude or confirm the presence of nocturnal polyuria.

Nocturnal polyuria is defined in children and adolescent age group as, urine production during the period of sleep which equals to or more than 130% of estimated bladder volume for age (EBV).⁽¹⁷⁾

Estimated bladder capacity for age is calculated by the formula [30 X (age in years + 2)] in ml. The amount of urine last voided before sleep is discarded and first morning voiding volume is

added to the calculated nocturnal urine volume. Clear instructions for mothers were to let the child void before sleep and every two hours till 8 am. Short intervals were meant to avoid enuretic episodes during calculation of nocturnal urine volume, and if occurred it mandates the repeat of chart on another day.

Nocturnal urine collected over the night was tested for osmolality, it was measured in mOsm/kg.

Serum Vitamin D level.

Vitamin D serum level was measures using the ELISA technique. The Cal Biotech Vitamin D Kit (Mannheim, Germany) was used, which is a solid phase enzyme linked immunoassay (ELISA), based on the principal of competitive binding. Vitamin D deficiency was defined as serum Vit. D below 20 ng/ml.

Sensitivity:

The sensitivity of this test kit is 0.67ng/ml. Sensitivity was determined by calculating the mean plus 2SD of the standard zero point tested 20 times in the same Statistical Methods run.

Statistical methods

The collected data were coded, tabulated, and statistically analyzed using IBM SPSS statistics (Statistical Package for Social Sciences) software version 28.0, IBM Corp., Chicago, USA, 2021. Quantitative data tested for normality using Shapiro-Wilk test, then described as mean \pm SD (standard deviation), and then compared using independent t-test. Qualitative data described as number and percentage and compared using Chi square test. Pearson test was used for correlations. ROC curve was used to evaluate the performance of variables to differentiate between conditions. The level of significance was taken at p-value <0.050 was significant, otherwise was non-significant.

Diagnostic characteristics was calculated as follows:

- Sensitivity = (True positive test / Total positive golden) x 100
- Specificity = (True negative test / Total negative golden) x 100
- Diagnostic accuracy = ([True positive test + True negative test] / Total cases) x 100
- Youden's index = sensitivity + specificity - 1
- Predictive positive value = (True positive test / Total positive test) x 100
- Predictive negative value = (True negative test / Total negative test) x 100
- Likelihood ratio positive (LR+) = (sensitivity / 1-specificity)
- Likelihood ratio negative (LR-) = (1- sensitivity / specificity)

Diagnostic odds ratio (DOR)= LR+/ LR-

Serum level of vitamin D, in monosymptomatic enuretic children and non-enuretic children: a comparative study

[name] [name]*, [name]. [name]*, [name] **, [name]*.

* Urology Department, Faculty of Medicine, Ain Shams University

** Damanhour National Medical Institute.

Corresponding Author:

[name] [name]

Associate professor of urology

Faculty of Medicine

Ain shams university

Email: [contact]

[contact]

[name], Faculty of medicine, El Demerdash hospital.

[name]

[contact]

Professor and chief of urology department

Faculty of medicine

Ain Shams university

[name]

[contact]

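### No age scaling is stated for average voided volume, so under the general t-test rule age spread would dilute the group comparison and an age imbalance could bias it (minor, secondary variable)

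*Combined protocol and SAP*

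**What the plan says.** All references are to the combined protocol and SAP.

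- **Patients and methods.** For cases: "Sixty children aged from 5 to 15 with primary mono-symptomatic nocturnal enuresis were included and selected randomly". For controls: "Sixty healthy children were included as a control group whose ages ranged from 5 to 15 years old". No age matching is described.
- **Methods, frequency-volume chart.** The chart is recorded in both groups "to evaluate frequency, average voided volume, and to exclude or confirm the presence of nocturnal polyuria". No unit, scaling or specific test is given for average voided volume.
- **Same section.** "Estimated bladder capacity for age is calculated by the formula [30 X (age in years + 2)] in ml". Nocturnal polyuria is defined against this quantity (EBV below), with a threshold of 130%.
- **Statistical methods.** Quantitative data are checked for normality, summarised as mean and SD, "and then compared using independent t-test". There is no covariate or stratification. On significance: "The level of significance was taken at p-value <0.050 was significant, otherwise was non-significant". Sidedness is not stated.
- **Aim of the study.** The aims concern vitamin D deficiency in relation to enuresis and to urine osmolality. Voided volume is not among them.

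**The concern.** The plan accepts that a urine volume has to be read against the child's age, and it builds that into the polyuria definition. It then leaves a second volume from the same chart without any stated scaling. If the general rule is applied as written, a 5-year-old and a 15-year-old enter the same t-test in ml.

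This has two consequences:

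- **Precision.** Even when the two groups have identical age distributions, the spread of volume with age adds to the SD, and a modest difference in voided volume becomes harder to see.
- **Bias.** If mean ages differ, part of the difference in ml is age alone. The Introduction puts enuresis at up to 15% of 5-year-olds and 10% of 10-year-olds, so cases could well be the younger group. An age artefact would then look like smaller voided volumes in enuretic children.

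**Working it through.** The plan states no power, SD or expected difference for this variable, so there is no figure of its own to reproduce.

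**Inputs from the documents:** 60 children per group; ages 5-15; EBV = 30 x (age + 2) ml; significance level 0.05 (two-sided assumed).

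**Assumptions not in the documents:** ages uniform over 5-15; volume V = k x EBV x (1 + CV x Z), with Z a standard normal variable and a within-age CV of 20-40%. The constant k cancels throughout and is set to 1.

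**Step 1: range of expected capacity.** At age 5, 30 x 7 = 210 ml. At age 15, 30 x 17 = 510 ml. The ratio is 510/210 = 2.43.

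**Step 2: spread that enters the t-test.** Mean EBV = 30 x (10 + 2) = 360 ml. SD of EBV = 30 x 10/sqrt(12) = 86.6 ml, a CV of 86.6/360 = 24%.

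Total SD in ml = sqrt(86.6^2 + CV^2 x (360^2 + 86.6^2)).

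At CV 25%: sqrt(7,500 + 0.0625 x 137,100) = 126.8 ml, so the total CV is 126.8/360 = 35.2%.

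**Step 3: effective sample size and age share of variance.** Effective n = 60 x (within-age CV / total CV)^2. Age share = 86.6^2 / total SD^2. The shift per year of mean age difference is 30 ml / total SD.

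| Within-age CV | Total SD (ml) | Total CV | Age share of variance | Effective n of 60 | 1-year age gap, in SD |
|---|---|---|---|---|---|
| 20% | 113.9 | 32% | 58% | 24 | 0.26 |
| 25% | 126.8 | 35% | 47% | 30 | 0.24 |
| 30% | 140.9 | 39% | 38% | 35 | 0.21 |
| 40% | 171.6 | 48% | 25% | 42 | 0.17 |

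With ages uniform over 5-11 instead (mean EBV 300 ml, SD 30 x 6/sqrt(12) = 52.0 ml), effective n rises to 34 / 40 / 44 / 49.

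**Step 4: power with equal ages in the two groups, CV 25%.** The noncentrality is difference x sqrt(30) / CV, with 118 degrees of freedom.

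- 10% difference: in ml, 0.10 x 5.477/0.352 = 1.56, power 34%. As % of EBV, 0.10 x 5.477/0.25 = 2.19, power 58%.
- 20% difference: 87% in ml, 99% as % of EBV.
- Difference detectable with 80% power: 2.80 x 0.352 x sqrt(1/30) = 18% in ml; 2.80 x 0.25 x sqrt(1/30) = 12.8% scaled.

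Across CVs of 40% down to 20%, a 20% difference has about 63-93% power in ml.

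**Step 5: unequal mean ages, no true age-specific difference, CV 25%.** The standard error of the difference is 126.8 x sqrt(2/60) = 23.1 ml. Mean age gaps of 0.5, 1 and 2 years shift the comparison by 15, 30 and 60 ml. The t-test in ml is then significant about 10%, 25% and 74% of the time instead of 5%.

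**The case against.** Several objections carry weight.

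- **The comparison is not written down.** The plan never says that average voided volume is tested between groups in ml. The only mention of ml in the chart section belongs to the capacity formula, and the t-test sentence names no variable. This stands: the comparison in ml is what the general rule would produce by default, not a stated intention.
- **A reader might infer that age swamps the group contrast.** The figures do not support that. The 2.43 ratio compares the two ends of the age range, whereas the CV of EBV entering the test is about 24%. Age is less than half of the variance in three of the four CV scenarios, and a 20% difference remains reasonably detectable in ml. The loss falls mainly on differences near 10%.
- **Proportionality is assumed.** EBV is an expected capacity and the variable is an average void. At night the child voids every two hours, so those volumes reflect urine output and schedule as well as capacity. The plan does not say which voids enter the average. This stands as a limit on the percentage scale and is a reason to offer age as a covariate as an alternative.
- **The bias needs unequal ages.** That belongs to the wider absence of age matching or adjustment, and no ages are reported to show that it occurred. The precision loss, however, remains even with perfectly balanced ages.
- **The variable is outside the aims.** This also stands, and it limits the importance of the point.

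**Conclusion.** The concern holds as a minor point about a secondary chart variable. Followed as written, the plan would compare average voided volume without allowing for age, although it scales nocturnal polyuria from the same chart.

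With ages uniform over 5-15, volume proportional to EBV and a within-age CV of 20-40%, 60 per group are worth about 24-42. Under the same assumptions a 1-year gap in mean age creates about 0.17-0.26 SD of spurious difference. The age distribution, the CV and the proportionality are not in the documents, and a narrower age range reduces the precision loss.

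A reader might also infer that the vitamin D or osmolality results are undermined. The documents do not support that on this ground: neither stated aim uses average voided volume, and the polyuria classification is already related to age.

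**What to change.** State in the Statistical methods how average voided volume is expressed and compared. Either divide each child's value by 30 x (age + 2) and compare the groups on that percentage, or compare ml with age as a covariate. Treat nocturnal urine volume the same way if it is reported as a quantity. Keep raw ml as description, and show the age distribution by group. It would also help to say which voids enter the average.

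The cost is one computed column or one added covariate, and a sentence or two in the methods. Age and volume are already needed for the polyuria classification, so no new measurement is required and the change can be made at analysis. The small downside is that the percentage scale relies on average voided volume rising roughly in step with expected capacity. The covariate version does not need strict proportionality, though it still assumes a form for the relation with age.

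### Does repeating the chart after a wet night bias nocturnal volume, polyuria and osmolality in the enuretic group enough to call for a change?

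*Combined protocol and SAP*

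**What the plan says.** Both groups keep a chart. On the chart night the child voids at bedtime and then two-hourly until the morning. The Methods give the reason: "Short intervals were meant to avoid enuretic episodes during calculation of nocturnal urine volume". If an episode happens anyway, "if occurred it mandates the repeat of chart on another day". Nocturnal polyuria is a night volume of at least 130% of estimated bladder volume for age (EBV). For osmolality the text says only "Nocturnal urine collected over the night was tested for osmolality". It does not say whether that is the first or the accepted night, and it does not ask for a count of repeats.

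The Aim has two parts: vitamin D deficiency in relation to enuresis, and to "study the correlation between vitamin D deficiency and urine osmolality". Cases enter with "bedwetting frequency of 3 or more nights per week"; controls are non-enuretic. The study was "conducted in the period between February 2021 and August 2021".

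**The concern.** The rule is worded for every child but can bind almost only in cases, so night selection differs between the groups. The Introduction states that "Nocturnal polyuria and decreased nocturnal urine osmolality were key factors in pathogenesis of nocturnal enuresis". If the same holds from night to night within a child, wet nights are the high-volume, dilute ones, and discarding them makes cases look more normal. Case-control differences in volume, polyuria and osmolality would shrink, and the second aim, which uses osmolality, could be touched as well. With no count of repeats, a reader cannot tell whether the effect is nil or material.

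**Working it through.** The plan gives no figure to reproduce: no repeat count, standard deviation or expected difference.

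**Inputs from the documents.** 60 cases and 60 controls; polyuria at 1.3 × EBV; voids every 2 hours; usual wetting on at least 3/7 = 43% of nights in cases.

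**How often would the rule bind?** At the polyuria threshold, over an assumed 8 to 10 hour night, the urine made between two voids is 1.3 × 2/8 = 0.325 to 1.3 × 2/10 = 0.26 of EBV. The bladder is far from full at each void, so wet chart nights should be much rarer than 43%.

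**Size, first model.** All inputs are assumed. Volume/EBV has mean 1.2, SD 0.25 between children and SD 0.25 between nights. The probability of wetting is logistic in volume, and nights are redrawn until dry. Osmolality in SD units is −0.8 × standardised volume plus noise. Vitamin D correlates −0.4 with the child's mean volume.

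| Output-wetting slope | First nights wet | Polyuria, first → accepted night | Children of 60 | Osmolality shift | Vitamin D–osmolality r |
|---|---|---|---|---|---|
| 0 (no link) | any | unchanged | 0 | 0 | unchanged |
| 4 (moderate) | 4.5% | 38.9% → 37.9% | 0.6 | +0.02 SD | 0.226 → 0.222 |
| 4 | 10% | 38.8% → 36.5% | 1.4 | +0.05 SD | 0.224 → 0.217 |
| 4 | 16% | 38.9% → 34.8% | 2.5 | +0.08 SD | 0.228 → 0.216 |
| 8 (steep) | 19% | 38.7% → 31.4% | 4.4 | +0.14 SD | 0.224 → 0.200 |

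The yardstick is the standard error of a mean difference with 60 per group: √(2/60) = 0.18 SD.

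**Size, second model.** Let p be the share of wet nights and ρ the within-child correlation of wetting liability with output. The mean shift on dry nights is −ρ·φ(c)/(1−p) within-child SDs, with c the (1−p) normal quantile. For p = 0.10 and ρ = 0.4, c = 1.28 and φ(c) = 0.175, so the shift is −0.4 × 0.175/0.90 = −0.078. With an assumed within-child SD of 80 ml that is about 6 ml. With a between-child SD of 100 ml the total SD is √(100² + 80²) = 128 ml, so the shift is about 0.05 SD. Over p = 0.05 to 0.20 and ρ = 0.2 to 0.6, with within-child SDs of 80 to 120 ml, volume is about 2 to 25 ml low and polyuria about 0.5 to 7 points low.

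**The correlation.** The first model gives a slight fall. The second, with solute load independent of volume, gives a slight rise (0.176 to 0.179 at p = 0.20, ρ = 0.4). Neither size nor direction supports a correction.

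**Would an alternative do better?**
- *Osmolality on whatever urine was caught on the first night, wet or dry.* This removes the selection only if the partial catch is unbiased. If the urine lost was more dilute than the urine caught, the reading is too high, in cases only, which is the same direction as the bias to be removed. In the first model it beats the present rule unless caught urine reads about 0.5 SD (slope 4) or 0.7 SD (slope 8) above the whole night. No figure in the documents shows which side applies. It also needs an extra assay for each wet night, and it leaves volume and polyuria selected as before.
- *Polyuria with and without children who needed a repeat.* At 10% wet about 6 of 60 cases have a repeat. Expected polyuria is 57% against 34% (slope 4), and Fisher's exact test on 6 against 54 children has only about 14% to 16% power to detect that. Leaving these children out gives 34%, further from the first-night 38.8% than the 36.5% obtained under the present rule.

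**The case for a change.** The best case for a change is that the size is unknown and could be larger. If two-hourly voiding barely helped and about 41% of chart nights were wet, the slope-4 model takes polyuria from 39.0% to 27.7% and osmolality up by 0.20 SD, more than one standard error. Small shifts also cost power: with 60 per group and 80% power at 0.51 SD, a loss of 0.05 SD leaves about 71%. Confirming or excluding polyuria is a stated purpose of the chart, and osmolality is in the second aim.

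Part of this stands. The selection is one-sided, its direction under the stated condition is clear, and a count of repeats would tell a reader how much it could matter. But the large figure needs chart nights about as wet as ordinary nights, which fits poorly with a bladder about a third full or less at each two-hourly void. The condition itself is not shown: the Introduction speaks of causes of enuresis, not of wet against dry nights in one child. It also describes low nocturnal ADH and osmolality as "linked to children who also suffer of arousal abnormality", so an episode may reflect a missed arousal and not a high-output night. Nor can first-night sampling be added to a study whose text describes collection in 2021.

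**Conclusion.** The observation is correct, but it does not call for a change to the plan. The bias exists only if wetting tracks nightly output within a child, and every size above rests on assumed inputs. With a moderate link and up to 16% wet chart nights it is at most about 2.5 of 60 cases for polyuria and 0.08 SD for osmolality, under half of one standard error; a steep link with 19% wet gives 4.4 cases and 0.14 SD. The serum vitamin D comparison is not touched, and the vitamin D–osmolality correlation moves by no more than 0.024 in these scenarios, with no robust direction.

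Repeating the chart is a fair trade-off: a complete volume on a dry night in place of an incomplete one on a wet night. The alternatives exchange one possible case-only bias for another, or check with too few children to inform. What remains is reporting that analysts would sensibly supply: the number of repeated charts by group where records exist, which night's urine was tested, and a sentence naming the selection of dry nights as a limitation. None of these alters a result.

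### Cases and controls are compared without matching, stated concurrent sampling or adjustment for sampling date, in a February-to-August study of a vitamin the document attributes mainly to sunlight

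*Combined protocol and SAP*

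**What the plan says.** The first item under Aim of the Study is "To evaluate the relationship between Vitamin D deficiency and nocturnal enuresis". Patients and Methods describes the design: "This is a case control study which was performed in Ain Shams University Hospitals". One period is given for the whole study, with no dates by group: "It was conducted in the period between February 2021 and August 2021".

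There are 60 cases, described as randomly selected, and 60 controls. Both groups cover ages 5 to 15. Of the controls we learn only that "they were chosen from apparently healthy non-enuretic children"; where and when they were recruited is not stated. Nothing is said about matching on age, sex or date.

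The Introduction states: "The source of vitamin D is primarily sunlight". The only restriction bearing on vitamin D exposure is the exclusion of "patients who are on vitamin D supplements". The outcome of interest uses one fixed cut-off all year: "Vitamin D deficiency was defined as serum Vit. D below 20 ng/ml".

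Under Statistical methods, data are summarised "and then compared using independent t-test. Qualitative data described as number and percentage and compared using Chi square test", with Shapiro-Wilk, Pearson correlation, ROC curves and diagnostic indices besides. None of these uses a covariate, stratum or matched pair, and sampling date is not named as a variable collected.

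**The concern.** The document itself names a determinant of vitamin D, sunlight, that can be expected to change between February and August. In a case-control comparison this matters only if the groups were sampled at different times. The plan neither prevents that (no matching, no stated parallel recruitment) nor corrects for it (no adjusted analysis), and without a table of dates it could not detect it. A shared age range is a restriction, not matching. Excluding supplement users deals with intake, not sun exposure.

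The first aim is at stake. If controls tended to be sampled later than cases, a purely seasonal difference could be read as an association with enuresis. If cases tended to be sampled later, a real association could be hidden. Any ROC or diagnostic index that uses vitamin D as the marker inherits the same problem.

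**Working it through.** The document gives no SD, effect size or power figure, so there is nothing of its own to reproduce. What follows is an illustration.

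**Inputs from the document:** 60 per group; significance at p < 0.050 (sidedness not stated, two-sided assumed); deficiency below 20 ng/ml.

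**Assumed inputs:** early-to-late gap G of 1 to 8 ng/ml; within-season SD of 8 to 12 ng/ml; difference q between groups in the share sampled late. The main cases are q = 0.2 (24 v 36 of 60 sampled late) and q = 0.3 (21 v 39). The mid case is G = 5, SD = 10.

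**1. Spurious mean difference = G × q.** Mid case: 5 × 0.2 = 1.0 and 5 × 0.3 = 1.5 ng/ml. Range: 0.2 to 1.6 at q = 0.2, and 0.3 to 2.4 at q = 0.3. For scale, 60 v 60 has 80% power for (1.96 + 0.84) × √(2/60) = 0.51 SD, or about 5.1 ng/ml at SD 10.

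**2. False-positive rate of the unadjusted t-test** (no true difference, fixed season counts, 20,000 runs; the range within a cell is SD 12 to SD 8):

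| Gap (ng/ml) | q = 0.2 | q = 0.3 |
|---|---|---|
| 1 | 5.2-5.5% | 5.3-5.6% |
| 3 | 5.4-6.6% | 6.8-9.0% |
| 5 | 6.6-9.2% (7.5% at SD 10) | 9.9-15.1% (11.6% at SD 10) |
| 8 | 9.6-13.7% | 16.6-29.5% |

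The top values are the corner where the gap equals a full SD. A separate simulation in SD units agrees at 20 points (7.6% at a gap of 0.5 SD, 13.7% at 1.0 SD). At 0.5 SD it gives 17.6% at 40 points and 35.7% at 60.

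**3. Odds ratio for deficiency from season alone.** Mid case, overall mean 20: the early mean is 17.5 and the late mean 22.5, so P(<20) = Φ(0.25) = 0.599 early and Φ(−0.25) = 0.401 late.
- q = 0.2: 0.6 × 0.599 + 0.4 × 0.401 = 0.520 in one group and 0.480 in the other; OR = (0.520/0.480)² ≈ 1.17.
- q = 0.3: 0.65 × 0.599 + 0.35 × 0.401 = 0.530 against 0.470; OR = (0.530/0.470)² ≈ 1.27.

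Over overall means of 16 to 26 ng/ml and the gaps and SDs above, the ranges are 1.03-1.37 and 1.04-1.60. The chi-square false-positive rate is 7.6% and 10.1% in the mid case, and over the four gap/SD pairs run it is 5.1-12.1% and 4.8-25.0%.

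**4. Masking.** With a true difference of 5 ng/ml, SD 10, gap 5 and cases sampled later, the expected difference falls to 5 − 1.0 = 4.0 or 5 − 1.5 = 3.5 ng/ml. T-test power is 76% with no imbalance, 56% at 20 points and 45% at 30 points.

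**5. Concurrent recruitment.** If each child's season is random with the same probability in both groups, the t-test rejects in 4.7-5.3% of runs and the chi-square test in 5.2-5.7%. With exactly equal season counts the t-test is slightly conservative (4.8% down to 2.6% as the gap rises from 0.25 to 1.0 SD). Neither is a bias.

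**6. With a season term.** The linear model with season, age and sex holds 4.7-5.2% throughout. The adjusted Wald test in the logistic model gives 4.3-6.2% at 20 and 30 points. Power in step 4 returns to 73-76% at 20 points and 69-74% at 30 points, across gaps of 1 to 8 ng/ml. If all cases were sampled in one period and all controls in the other, group and season cannot be separated and no model helps.

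**The case against.** The strongest reply is that the harm depends on something the document does not show. One window covers both groups, all children had the same work-up, and the natural reading is that both were enrolled over the same months. On that view this is a reporting gap.

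The sizes also rest wholly on assumed gaps, SDs and imbalances. At 10 points of imbalance (gap 5, SD 10) the rate is 5.0-5.6%, essentially nominal. Since the first aim concerns deficiency, the chi-square rates (7.6% and 10.1%) are closer to the point than the t-test rates, and they are a little smaller. A split at mid-May is a crude stand-in for sun exposure.

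Most of this is fair as a limit. Confounding is possible, not demonstrated, and small imbalances or gaps do little. Two narrower points also stand. The vitamin D-osmolality correlation is affected by date only if osmolality varies with date too, which the document does not say. Imbalance in age or sex could be seen with the listed tests, and the document gives no vitamin D link for either.

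What does not stand is that a shared window settles the matter: it does not establish parallel sampling within seven months. Nor does the choice of test change the conclusion, since both err in the same direction.

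**Conclusion.** The concern holds. For the first aim, confounding by sampling date is left open by the design, uncorrected by every listed analysis and not detectable from any planned output. Whether it occurred cannot be told from the text supplied.

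If recruitment was concurrent, the planned tests are sound. If the late-sampled share differed by 20 to 30 points and the seasonal gap was about half an SD, the nominal 5% error becomes roughly 8-12% by t-test or 8-10% by chi-square, with a spurious odds ratio of 1.17-1.27 or a comparable masking effect. With a 1 ng/ml gap the t-test rate is only 5-6%; at a full-SD gap it reaches 14-29%. The omission is certain and its consequence conditional, so this should be corrected, with medium confidence that it affects the result.

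**What to change.** 1. Tabulate sampling month, age and sex by group, and state whether the groups were recruited in parallel. If timing is balanced, this table answers most of the concern.
2. For the first aim, report one logistic regression of case status on deficiency (<20 ng/ml), adjusted for sampling season (one early/late term split at mid-May, the middle of the window), age and sex, with the adjusted odds ratio and 95% CI. Age and sex enter as routine covariates.
3. Support it with a linear regression of continuous vitamin D on group with the same covariates, and keep the unadjusted tests as descriptive.
4. If the table shows that the groups hardly overlap in time, say that the comparison cannot be separated from season.

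**Cost.** Sampling dates must be retrieved; the document does not say they were recorded. The standard error of the log odds ratio widens by about 2-17% over all runs: 2-4% when timing is balanced and season is weak to moderate, more when season strongly predicts deficiency or timing is unbalanced. A single early/late term can leave some date confounding within each half. The text is in the past tense, so if the data have already been analysed the model must be labelled post hoc.
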